9.0 EVALUATIONS DURING THE STUDY

Cycle 1 Day 1 (Rituximab and Lirilumab)

1. CBC, platelet count and differential, sodium, potassium, calcium, BUN, creatinine, glucose, phosphorous, magnesium, albumin, total protein, alkaline phosphatase, total bilirubin, ALT, AST, uric acid, LDH
2. Vital signs, history and physical examination (Note: history and physical examination within 3 days prior to the Day 1 is acceptable)

Cycle 1 Day 8 (Rituximab) (+/- 2 day)

1. CBC, platelet count and differential, sodium, potassium, calcium, BUN, creatinine, glucose, phosphorous, magnesium, albumin, total protein, alkaline phosphatase, total bilirubin, ALT, AST, uric acid, LDH
2. Vital signs, history and physical examination

Cycle 1 Day 15 (Rituximab) (+/- 2 day)

1. CBC, platelet count and differential, sodium, potassium, calcium, BUN, creatinine, glucose, phosphorous, magnesium, albumin, total protein, alkaline phosphatase, total bilirubin, ALT, AST, uric acid, LDH
2. Vital signs, history and physical examination

Cycle 1 Day 22 (Rituximab) (+/- 2 day)

1. CBC, platelet count and differential, sodium, potassium, calcium, BUN, creatinine, glucose, phosphorous, magnesium, albumin, total protein, alkaline phosphatase, total bilirubin, ALT, AST, uric acid, LDH
2. Vital signs, history and physical examination

Cycle 2 Day 1 (Rituximab and Lirilumab) (+/- 1 week)

1. CBC, platelet count and differential, sodium, potassium, calcium, BUN, creatinine, glucose, phosphorous, magnesium, albumin, total protein, alkaline phosphatase, total bilirubin, ALT, AST, uric acid, LDH, serum immunoglobulins, TSH, Free T4
2. B, T, NK cell counts and subset analyses on the peripheral blood
3. Serum or urine β -hCG pregnancy test (for women of childbearing potential)
4. Vital signs, history and physical examination

Cycle 2 Day 8 (no mAb) (+/- 2 day)

1. CBC, platelet count and differential, sodium, potassium, calcium, BUN, creatinine, glucose, phosphorous, magnesium, albumin, total protein, alkaline phosphatase, total bilirubin, ALT, AST, uric acid, LDH

Cycle 2 Day 15 (no mAb) (+/- 2 day)

1. CBC, platelet count and differential, sodium, potassium, calcium, BUN, creatinine, glucose, phosphorous, magnesium, albumin, total protein, alkaline phosphatase, total bilirubin, ALT, AST, uric acid, LDH
2. Vital signs, history and physical examination

Cycle 2 Day 22 (no mAb) (+/- 2 day)

1. CBC, platelet count and differential, sodium, potassium, calcium, BUN, creatinine, glucose, phosphorous, magnesium, albumin, total protein, alkaline phosphatase, total bilirubin, ALT, AST, uric acid, LDH

Cycle 3 Day 1 (Rituximab and Lirilumab) (+/- 1 week)

1. CBC, platelet count and differential, sodium, potassium, calcium, BUN, creatinine, glucose, phosphorous, magnesium, albumin, total protein, alkaline phosphatase, total bilirubin, ALT, AST, uric acid, LDH, serum immunoglobulins, TSH, Free T4
2. B, T, NK cell counts and subset analyses on the peripheral blood
3. Serum or urine β -hCG pregnancy test (for women of childbearing potential)
4. Vital signs, history and physical examination

Cycle 3 Day 15 (no mAb) (+/- 3 day)

1. CBC, platelet count and differential, sodium, potassium, calcium, BUN, creatinine, glucose, phosphorous, magnesium, albumin, total protein, alkaline phosphatase, total bilirubin, ALT, AST, uric acid, LDH
2. Vital signs, history and physical examination

End of Cycle 3 (response assessment) (+/- 1 week)

1. CBC, platelet count and differential, sodium, potassium, calcium, BUN, creatinine, glucose, phosphorous, magnesium, albumin, total protein, alkaline phosphatase, total bilirubin, ALT, AST, uric acid, LDH, β -2 microglobulin, serum immunoglobulins
2. Vital signs, History and Physical Examination
3. B, T, NK cell counts and subset analyses on the peripheral blood
4. TSH, Free T4
5. Serum or urine β -hCG pregnancy test (for women of childbearing potential)
6. Bone marrow aspiration and biopsy with multi-color flow cytometry for MRD evaluation
7. CT scan of the neck (if indicated), chest, abdomen, and pelvis with IV and oral contrast. PET scan may be used instead of the CT scan imaging.

Cycle 4 Day 1 (Rituximab and Lirilumab) (+/- 1 week)

1. CBC, platelet count and differential, sodium, potassium, calcium, BUN, creatinine, glucose, phosphorous, magnesium, albumin, total protein, alkaline phosphatase, total bilirubin, ALT, AST, uric acid, LDH
2. Serum or urine β -hCG pregnancy test (for women of childbearing potential)
3. Vital signs, history and physical examination

Cycle 4 Day 15 (no mAb) (+/- 3 day)

1. CBC, platelet count and differential, sodium, potassium, calcium, BUN, creatinine, glucose, phosphorous, magnesium, albumin, total protein, alkaline phosphatase, total bilirubin, ALT, AST, uric acid, LDH
2. Vital signs, history and physical examination

Cycle 5 Day 1 (Rituximab and Lirilumab) (+/- 1 week)

1. CBC, platelet count and differential, sodium, potassium, calcium, BUN, creatinine, glucose, phosphorous, magnesium, albumin, total protein, alkaline phosphatase, total bilirubin, ALT, AST, uric acid, LDH, serum immunoglobulins, TSH, Free T4
2. B, T, NK cell counts and subset analyses on the peripheral blood
3. Serum or urine β -hCG pregnancy test (for women of childbearing potential)
4. Vital signs, history and physical examination

Cycle 5 Day 15 (no mAb) (+/- 3 day)

1. CBC, platelet count and differential, sodium, potassium, calcium, BUN, creatinine, glucose, phosphorous, magnesium, albumin, total protein, alkaline phosphatase, total bilirubin, ALT, AST, uric acid, LDH
2. Vital signs, history and physical examination

Cycle 6 Day 1 (Rituximab and Lirilumab) (+/- 1 week)

1. CBC, platelet count and differential, sodium, potassium, calcium, BUN, creatinine, glucose, phosphorous, magnesium, albumin, total protein, alkaline phosphatase, total bilirubin, ALT, AST, uric acid, LDH, serum immunoglobulins, TSH, Free T4
2. B, T, NK cell counts and subset analyses on the peripheral blood
3. Serum or urine β -hCG pregnancy test (for women of childbearing potential)
4. Vital signs, history and physical examination

Cycle 6 Day 15 (no mAb) (+/- 3 day)

1. CBC, platelet count and differential, sodium, potassium, calcium, BUN, creatinine, glucose, phosphorous, magnesium, albumin, total protein, alkaline phosphatase, total bilirubin, ALT, AST, uric acid, LDH
2. Vital signs, history and physical examination

End of Cycle 6 (response assessment) (+/- 1 week)

1. CBC, platelet count and differential, sodium, potassium, calcium, BUN, creatinine, glucose, phosphorous, magnesium, albumin, total protein, alkaline phosphatase, total bilirubin, ALT, AST, uric acid, LDH, β -2 microglobulin, serum immunoglobulins
2. Vital signs, History and Physical Examination
3. B, T, NK cell counts and subset analyses on the peripheral blood
4. TSH, Free T4
5. Serum or urine β -hCG pregnancy test (for women of childbearing potential)
6. Bone marrow aspiration and biopsy with multi-color flow cytometry for MRD evaluation
7. CT scan of the neck (if indicated), chest, abdomen, and pelvis with IV and oral contrast. PET scan may be used instead of the CT scan imaging.

Cycle 7 onwards (All evaluations can be +/- 1 week) (Rituximab on day 1 of cycles 7-12; Lirilumab on day 1 of cycles 7-24)

1. CBC, platelet count and differential; serum sodium, potassium, calcium, BUN, creatinine, glucose, phosphorous, magnesium, albumin, total protein, alkaline phosphatase, total bilirubin, ALT, AST, uric acid, LDH at least monthly.
2. Complete history and physical examination including vital signs at least monthly.
3. Quantitative immunoglobulin levels every month
4. B, T, NK cell counts and subset analyses on the peripheral blood every 3 months
5. TSH, Free T4 every 3 months
6. Serum or urine β -hCG pregnancy test (for women of childbearing potential) before dose of lirilumab
7. Urinalysis every 3 months
8. Bone marrow aspiration and biopsy with multi-color flow cytometry for MRD evaluation every 3 months
9. CT scan of the neck (if indicated), chest, abdomen, and pelvis with IV and oral contrast every 3 months. PET scan may be used instead of the CT scan imaging.

End of Study Visit – Patients, who are taken off study for any reason, will have an end of study visit. The end of study visit will occur 30 days (+/- 1 week) after the last dose of the study drugs. At this visit, the patient will have labs (CBC, platelet count and differential, sodium, potassium, calcium, BUN, creatinine, glucose, phosphorous, magnesium, albumin, total protein, alkaline phosphatase, total bilirubin, ALT, AST, uric acid, LDH), history and physical examination, serum immunoglobulins, B, T, NK cell counts and subset analyses on the peripheral blood, bone marrow aspiration and biopsy with multi-color flow cytometry for MRD evaluation (if the previous bone marrow evaluation was >3 months ago), and CT or PET imaging (if the previous CT or PET imaging was >3 months ago).

After completion of all protocol related treatments, patients will be followed for at least one year with at least monthly labs (CBC, platelet count and differential, sodium, potassium, calcium, BUN, creatinine, glucose, phosphorous, magnesium, albumin, total protein, alkaline phosphatase, total bilirubin, ALT, AST, uric acid, LDH), at least monthly history and physical examination, serum immunoglobulins every 3 months, B, T, NK cell counts and subset analyses on the peripheral blood every 3 months, bone marrow aspiration and biopsy with multi-color flow cytometry for MRD evaluation every 3-6 months, and CT or PET imaging every 3-6 months. All evaluations can be +/- 1 week. Note: This post-protocol follow-up period of one year will end early if the patient starts another treatment for their CLL/SLL. Inability to comply with these post-protocol follow-up evaluations will not be considered a protocol-deviation.

NOTE: All treatments with lirilumab and rituximab must be administered at the MDACC. During the first cycle all laboratory evaluations will be done at MDACC. Subsequently, the patient may have laboratory work and physical examination done at a local clinic and the results reported to the research nurse for the study. The laboratory work done at a local clinic will be

forwarded to the patient's attending physician at MDACC, or PI of the study, who will sign off on the labs to verify that the results have been reviewed.

Outside Physician Participation During Treatment

1. MDACC Physician communication with the outside physician is required prior to the patient returning to the local physician. This will be documented in the patient record
2. A letter to the local physician outlining the patient's participation in a clinical trial will request local physician agreement to supervise the patient's care (Appendix D)
3. Protocol required evaluations outside MDACC will be documented by fax. Faxed evaluations will be dated and signed by the MDACC physician/investigator indicating that they have reviewed it.
4. A copy of the informed consent, protocol abstract, treatment schema and evaluation during treatment will be provided to the local physician.
5. Documentation to be provided by the local physician will include progress notes, reports of protocol required laboratory and diagnostic studies and documentation of any hospitalizations.
6. The home physician will be requested to report to the MDACC physician/investigator all life threatening events within 24 hours of documented occurrence.

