3.0 STUDY POPULATION

3.1 Inclusion Criteria

1. Patients will have a diagnosis of CLL or SLL who meet one or more criteria for active disease as defined by the International Working Group for CLL (IWCLL) and are:
 - a. Cohort 1: refractory to and/or relapsed after at least one prior therapy OR
 - b. Cohort 2: untreated patients with high-risk molecular features such as del(17p), mutated *TP53*, del(11q), unmutated *IGHV* gene, or are >65 years of age
2. Age 18 years or older
3. Eastern Cooperative Oncology Group (ECOG) Performance Status ≤ 2
4. Patients must have adequate renal and hepatic function
 - Serum bilirubin ≤ 1.5 x upper limit of normal (ULN). For patients with Gilbert's disease, serum bilirubin up to ≤ 3 x ULN is allowed provided normal direct bilirubin.
 - Serum creatinine ≤ 1.5 x ULN
 - ALT and AST ≤ 3 x ULN
5. Females of childbearing potential must have a negative serum or urine beta human chorionic gonadotrophin (β -hCG) pregnancy test result within 24 hours prior to the first dose of treatment and must agree to use an effective contraception method during the study and for 12 months following the last dose of the study drugs. Females of non-childbearing potential are those who are postmenopausal greater than 1 year or who have had a bilateral tubal ligation or hysterectomy. Males who have partners of childbearing potential must agree to use an effective contraceptive method during the study and for 31 weeks following the last dose of study drugs.
6. Patients or their legally authorized representative must provide written informed consent.

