6.0 DOSE DELAYS AND MODIFICATIONS

Patients who experience Grade 3 or 4 toxicity that can be clearly attributed to either lirilumab or to rituximab may continue treatment with the other agent while the causative agent is delayed until resolution of toxicity to grade ≤ 1 or baseline. In cases where Grade 3 or 4 toxicity cannot be attributed to a specific study drug, both study drugs should be held regardless of attribution of toxicity until the toxicity is resolved to grade ≤ 1 or baseline.

Rituximab and lirilumab administration should be delayed and increased monitoring of patients should ensue if any of the following drug-related adverse event(s) occurs:

- Any Grade ≥ 2 ALT, AST, or total bilirubin
- Any Grade ≥ 2 non laboratory non-skin drug related adverse event except for fatigue
- Any Grade ≥ 2 endocrine drug-related adverse event
- Any Grade ≥ 3 skin drug related adverse event
- Any Grade ≥ 3 drug-related laboratory abnormality (except lymphopenia or any electrolyte abnormality without any clinical sequelae that is either spontaneously reversible or resolves with clinical management to grade 2 or less within 72 hours)
- Any AE, laboratory abnormality or inter-current illness, which in the judgment of the investigator, warrants delaying the dose of study medication

Discontinuation of lirilumab will occur in the following situations:

- AST, ALT, or T Bili \geq Grade 3
- Grade 2 AST or ALT and symptomatic liver inflammation (e.g., right upper quadrant tenderness, jaundice)
- AST or ALT $> 3 \times$ ULN and concurrent total bilirubin $> 2 \times$ ULN in the absence of evidence of cholestasis (Hy's law)

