12.0 DISCONTINUATION OF STUDY TREATMENT

A patient's treatment with study drugs may be discontinued for any of the following reasons:

- Clinically significant progressive disease
- Adverse events that are not manageable with dose adjustments and/or optimal medical management, or that, in the opinion of the investigator, pose an unacceptable risk for the patient.
- Investigator decision
- Patient decision (e.g., withdrawal of consent)
- Study termination by Sponsor

Patients who experience toxicity that can be clearly attributed to either lirilumab or rituximab may continue treatment with the other agent. If toxicity cannot be clearly attributed to a single agent, treatment with both agents should be discontinued. Patients who discontinue treatment for reasons other than progressive disease should remain on study and continue to have disease assessments per protocol.

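### From Cycle 7 the pregnancy test is tied to the lirilumab dose alone, so a woman continuing on rituximab alone can receive up to five doses (Cycles 8 to 12) with no scheduled test

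*Combined protocol and SAP*

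**What the plan says.** Section 8.0 asks for a negative β-hCG within 24 hours before the first dose of study drugs. Section 9.0 then lists a β-hCG for women of childbearing potential on Day 1 of each of Cycles 2 to 6 and at End of Cycle 3 and End of Cycle 6. None of these entries names a drug.

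From Cycle 7 the trigger changes. Item 6 of that block lists the "pregnancy test (for women of childbearing potential) before dose of lirilumab", while the heading of the same block gives the dosing as "Rituximab on day 1 of cycles 7-12; Lirilumab on day 1 of cycles 7-24".

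Two sections allow a patient to be on one drug only. Under section 6.0, a patient whose Grade 3 or 4 toxicity is plainly due to one drug "may continue treatment with the other agent while the causative agent is delayed until resolution of toxicity". Section 12.0 says: "Patients who experience toxicity that can be clearly attributed to either lirilumab or rituximab may continue treatment with the other agent". Section 6.0 also has a list of liver findings headed "Discontinuation of lirilumab will occur in the following situations", with no equivalent discontinuation list for rituximab.

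Two safeguards apply throughout. Section 3.1 says women of childbearing potential "must agree to use an effective contraception method during the study and for 12 months following the last dose of the study drugs", and the Cycle 7 onwards block requires "Complete history and physical examination including vital signs at least monthly".

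**The concern.** For a woman on both drugs the wording makes no difference, because both are given on Day 1 and the lirilumab test serves for rituximab too. For a woman on lirilumab alone, a test precedes every dose. For a woman on rituximab alone, the section 9.0 text schedules no test from Cycle 7 on, and no reason is given for treating the two drugs differently. Elsewhere the protocol treats both as relevant to pregnancy: the pretreatment test and the contraception period refer to the study drugs together.

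Pregnancy is an exclusion criterion (section 3.2, item 15). Section 11.1.5 handles it as a serious adverse event and requires a report to the supporting company within 24 hours. These duties depend on the pregnancy being recognised. In the rituximab-alone case, recognition would rest on contraception, history and examination, whereas in Cycles 2 to 6 the protocol adds a test.

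**Working it through.** The plan states no figure on this point, so there is none to reproduce. The check is a count of doses and days from the schedule.

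**Inputs.** Cycles last 4 weeks (section 4.1). Rituximab is given on Day 1 of Cycles 7 to 12 (section 9.0). The last test not tied to lirilumab is at End of Cycle 6 (section 9.0).

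**Nominal days.** Day 1 of Cycle n falls on study day 28(n − 1) + 1. End of Cycle 6 is 6 × 28 = Day 168.

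**Case A: last lirilumab dose at or before Cycle 6, rituximab continued to Cycle 12**

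| Rituximab dose | Study day | Days since Day 168 test |
|---|---|---|
| C7 | 169 | 1 |
| C8 | 197 | 29 |
| C9 | 225 | 57 |
| C10 | 253 | 85 |
| C11 | 281 | 113 |
| C12 | 309 | 141 |

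Six doses follow the last scheduled test. The C7 dose comes nominally one day after it and is in effect covered. Five doses (C8 to C12) have no test within the preceding four weeks. Test and dose each have a window of ±1 week, so the 29 days could be 15 to 43 (29 ± 14) and the 141 days could be 127 to 155 (141 ± 14).

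**Case B: last lirilumab dose at Cycle k, k = 7 to 12.** The last test is then at CkD1 and 12 − k rituximab doses follow untested: 5, 4, 3, 2, 1 and 0. The maximum is again five.

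**Case C: one lirilumab dose held, for example C8 only.** One rituximab dose has no test, and the interval between tests is 225 − 169 = 56 days instead of 28.

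**Comparison with Cycles 2 to 6.** Every Day 1 visit has a test there, so the interval is 28 days or less whichever drug is given.

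**After the change.** With a test before each dose of either drug from Cycle 7, the number of doses without a test falls from five to zero.

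**The case against.** The case against has several parts.

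- **The wording fits the planned course.** Lirilumab is due on every Day 1 from Cycle 7 to 24, so a test before lirilumab covers every planned dosing day of both drugs. This is true, and it confines the gap to patients who depart from the plan. But sections 6.0 and 12.0 provide for exactly that departure.
- **The route to rituximab alone is narrow.** A reader might infer from the lirilumab-only discontinuation list that liver toxicity leaves rituximab running. The documents do not support that. Section 6.0 delays both drugs for drug-related Grade 2 or higher ALT, AST or bilirubin and for most Grade 2 or higher non-laboratory, non-skin events. Section 12.0 stops both when toxicity cannot be assigned to one drug. This stands and reduces the number affected. It does not close the gap, because a delay ends on recovery and rituximab may then resume without lirilumab.
- **Unseen documents may require a test.** The Schedule of Evaluations attachment and the institutional rituximab guidelines (section 5.2) were not available. This stands as a limit: the point concerns the section 9.0 text. If the attachment does require a test, the two should be made to agree.
- **A test before every dose exceeds the protocol's own standard,** since the C1 Day 8, 15 and 22 rituximab doses have none. From Cycle 7, however, there is one dosing day per cycle, so the change only restores the Cycles 2 to 6 frequency.
- **Investigators may test anyway.** Nothing forbids it, but nothing schedules it.

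**Conclusion.** The gap is real in the section 9.0 text and small: at most five rituximab doses (C8 to C12, 29 to 141 nominal days after the last scheduled test) for a woman who stays on rituximab after stopping lirilumab. It rests on 28-day cycles, no rituximab delays, and the absence of a testing rule in the documents not seen.

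The number of women of childbearing potential is not given. It is probably low, as the background section puts median age at diagnosis at 72. Purely as an assumption, if 2% to 10% of the maximum 48 patients are of childbearing potential and 2% to 10% of those continue on rituximab alone, the expected number is 48 × 0.02 × 0.02 = 0.02 to 48 × 0.10 × 0.10 = 0.5. The primary endpoint and stopping rules are not touched.

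Two stronger readings do not hold. Counting six uncovered doses ignores the test one day before the C7 dose. A reader might also take the absence of β-hCG and TSH/Free T4 from the End of Study list as a defect. A β-hCG there informs no dosing decision, and the contraception duty already runs for 12 months. For thyroid function, a last dose at C7, C8 or C9 Day 1 gives 169, 197 or 225 + 30 − 168 = 31, 59 or 87 days from the End of Cycle 6 test to End of Study. That is within or near the protocol's own three-monthly interval (84 days as three cycles, about 91 as calendar months).

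**What to change.** Reword item 6 of the Cycle 7 onwards list so that the β-hCG is done before each dose of study drug (lirilumab or rituximab), and make the Schedule of Evaluations say the same. No change to the End of Study list is needed.

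The cost is a wording change and at most six extra pregnancy tests (C7 to C12) for an affected woman. Women on both drugs or on lirilumab alone have no extra tests. The abstract shows this version as terminated, so the practical value now lies mainly in any reuse of the schedule.

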10.0 CRITERIA FOR RESPONSE

Response will be assessed by the investigator, based on physical examinations, CT scans, laboratory results, and bone marrow examinations, based on the 2008 IWCLL criteria for response for CLL. Overall response (OR) includes complete remission (CR), CR with incomplete marrow recovery (CRi) or partial remission (PR) as determined by investigator assessment using CLL response criteria.³⁰ Minimal residual disease (MRD) will be assessed in bone marrow by multi-color flow cytometry. Patients with missing or no response assessments will be classified as non-responders by intent to treat analysis.

